- Cisplatin is one of the most effective chemotherapeutic agents for ACC. In the Surgery Branch we have conducted Phase I and II trials using heated intraperitoneal (IP) chemotherapy with cisplatin for primary peritoneal mesothelioma, low grade appendiceal adenocarcinoma, ovarian malignancies, and high grade adenocarcinoma of the gastrointestinal tract. Synergy has been demonstrated for cisplatin and hyperthermia
- The purpose of this trial is to determine if an aggressive surgical approach with intraperitoneal administration of heated cisplatin when tumor volume is minimal, can impact and improve on progression free survival.

Objective:

- To determine IP progression free survival after optimal debulking and heated IP chemotherapy with cisplatin in patients with IP spread of adrenocortical cancer

Eligibility:

- Histologically proven ACC evaluable by CT imaging with the majority of disease confined to the peritoneal cavity and surgically resectable to a residual size of less than 1 cm or amenable to radiofrequency ablation in patients who are > 18 years of age.

Design:

- This is a classic phase 2 trial to determine efficacy of this therapeutic strategy in ACC. Patients will undergo cytoreductive surgery to achieve a CCR of 0 or 1. Patients who are successfully debulked will then undergo HIPEC with cisplatin. Patients will be evaluated by associate investigators in coordination with the Principal Investigator for eligibility. Due to its exploratory nature, up to 30 patients may be enrolled to obtain 24 evaluable patients. (Patients must undergo successful debulking and HIPEC to be considered evaluable.)

TABLE OF CONTENTS

PRECIS	3
TABLE OF CONTENTS.....	4
1 INTRODUCTION.....	6
1.1 Study objectives	6
1.2 Background and Rationale	6
2 ELIGIBILITY ASSESSMENT AND ENROLLMENT	9
2.1 Eligibility Criteria	9
2.2 Screening Evaluation.....	11
2.3 Registration Procedures.....	12
2.4 Stratification Procedures	12
3 STUDY IMPLEMENTATION	12
3.1 Study Design	12
3.2 Preoperative Patient Management.....	12
3.3 Patient Management in the Operating Room	13
3.4 Peritoneal metastasectomy and cytoreductive surgery.....	13
3.5 Intraperitoneal Chemotherapy HIPEC	13
3.6 Medications	14
3.7 Post-Operative Care	14
3.8 Research Evaluations	15
3.9 Discharge.....	15
3.10 Post Discharge.....	15
3.11 Treatment Assessment and Response (Follow up period)	15
3.12 Measurement of Health Related Quality of Life	16
3.13 Criteria for Removal from Protocol Therapy and Off Study Criteria	17

1 INTRODUCTION

1.1 STUDY OBJECTIVES

1.1.1 Primary Objective

- To determine intraperitoneal progression free survival after optimal debulking and heated intraperitoneal chemotherapy with cisplatin in patients with intraperitoneal spread of adrenocortical cancer

1.1.2 Secondary Objectives

- Determine morbidity of this procedure in this patient population
- Determine the impact of surgery and HIPEC on QOL
- Determine the impact of surgery and HIPEC on hormone excess
- Examine patterns of recurrence (local versus systemic)
- Perform molecular analyses to try to discern if there are intrinsic differences between tumors that recur widely throughout the peritoneal surface and those that metastasize to other organs or are confined to a local recurrence.
- Determine overall survival after optimal debulking and heated intraperitoneal chemotherapy with cisplatin in patients with intraperitoneal spread of adrenocortical cancer.

1.2 BACKGROUND AND RATIONALE

1.2.1 Adrenocortical Carcinoma

Adrenocortical carcinoma (ACC) is a rare tumor with an incidence of 1.5 to 2 per million people per year¹⁻³. It has a very poor prognosis with an overall 5-year mortality rate of 75 - 90% and an average survival from the time of diagnosis of 14.5 months. Signs and symptoms due to excess hormonal secretion are seen in a large fraction of patients, further contributing to the morbidity associated with this disease.

The treatment of choice for a localized primary or recurrent tumor is surgical resection. Excisable primary tumors represent about 40% of cases at presentation; however, 60 - 80% of these patients eventually die from recurrent extensive metastases⁴. Patients with recurrent or metastatic disease are infrequently curable by surgery alone due to the propensity for intraperitoneal recurrence.

For unresectable metastatic or recurrent disease, mitotane, aminoglutethimide, metapyrone, and ketoconazole are used. Of these, mitotane is the only agent with both anti-tumor and adrenolytic effects. Aminoglutethimide, metapyrone, and ketoconazole are used to treat the symptoms of excess hormone production in patients with functional tumors. Mitotane, the most extensively studied agent, was reported to have response rates of 30-60% in older studies without standardized response criteria or the use of modern imaging technology⁵⁻⁷. Response rates of 20% or less have been noted with more modern imaging technology. These responses persist for an average of 10.5 months with no apparent impact on overall survival.

Most reports of cytotoxic therapy for ACC are anecdotal or include a small number of patients⁸⁻¹³. These studies report low response rates with the majority of responses classified as partial and

of less than one year in duration. Trials using mitotane in combination with various chemotherapeutic agents have had similar results^{12, 13}. The largest randomized trial for metastatic or locally advanced ACC conducted was recently published and showed that a regimen of etoposide, doxorubicin and cisplatin (EDP) combined with mitotane was superior to the combination of streptozocin and mitotane with a median PFS of 5.0 months vs. 2.1 months and response rate of 23.2 and 9.2% respectively¹⁴.

A retrospective analysis was performed on fourteen patients with peritoneal predominant recurrences who were treated with EDP by [name] group at the NCI. Patients who did not respond to chemotherapy *survived an average of 14 months* following treatment; patients who demonstrated a response to the chemotherapy survived for an *average of 30 months*. While small, the numbers seem to indicate that response to chemotherapy may correlate with an increase in survival. Intraperitoneal chemotherapy allows the administration of high doses of chemotherapy directly to the tumor bed and thus may improve the progression free survival as well as overall survival in this patient population.

[name] group has also accumulated a large data base on metastatic adrenal cancer that includes whole exome sequence, as well as cDNA and microRNA array data. Preliminary data has shown a high level of expression of the chemokine receptor, CXCR4, on the membrane of adrenal cancer cells, and expression of the receptor's ligand, CXCL12 (SDF1) on the peritoneal surface. Because this finding may lead to a therapeutic option in the future, it will be further investigated during the course of this study as listed below.

1.2.2 Enumeration of Circulating Endothelial Cells (CEC)

Early increase of CEC following anti-angiogenic drug administration can be an interesting marker of treatment efficacy. Interpretation of CEC change must take into account multiple factors such as the mechanism of drug action, time of CEC measurement to drug administration, phenotype of CEC quantified. Theoretically, various antigens can be used to characterize mature CEC. In general CD45 expression is used to exclude hematopoietic cells, and CD133 to exclude immature cells. Commonly used endothelial markers include CD31, CD146, CD34, CD144 or CD105. However, there is a lack of consensus regarding combination of these markers to characterize CEC by flow cytometry analysis. In this study, we will evaluate pre- and post-treatment changes in mature circulating endothelial cells (CD 146+, CD133-), as determined by flow cytometry analysis. This evaluation will be conducted in [name] lab, NIH/NCI/MOB. CEC may be collected (16ml in CPT blue/black tubes) pre surgery, at 6 weeks (+/- 2 weeks) and 6 months (+/- one month).

During the course of this study, tissue will be procured at the time of surgery and will undergo molecular analysis in order to try to discern if there are intrinsic differences between tumors that recur widely throughout the peritoneal surface and those that metastasize to other organs or are confined to a local recurrence.

1.2.3 HIPEC for ACC

Cisplatin is one of the most effective chemotherapeutic agents for ACC. In the Surgery Branch we have conducted Phase I and II trials using heated intraperitoneal chemotherapy with cisplatin for primary peritoneal mesothelioma, low grade appendiceal adenocarcinoma, ovarian malignancies, and high grade adenocarcinoma of the gastrointestinal tract. Synergy has been demonstrated for cisplatin and hyperthermia¹⁵ and this was the basis for exploring the continuous

hyperthermic peritoneal perfusion with cisplatin in our initial Phase I trial. The dose-limiting toxicity in that trial was renal insufficiency related to systemic absorption of cisplatin and occurred at a dose of 350 mg/M². All subsequent Surgery Branch trials using Cisplatin as the HIPEC agent were conducted using 250 mg/m² with a thiosulfate bolus given 20 minutes before adding cisplatin to the intraperitoneal perfusate followed by continuous infusion of thiosulphate for an additional 12 hours.

We have used heated cisplatin in different histologies including primary peritoneal mesothelioma, low grade mucinous adenocarcinoma (including low grade mucinous neoplasms of borderline malignant potential), and adenocarcinoma of gastrointestinal tract origin however, the majority of our experience has been in intraperitoneal mesothelioma and low grade appendiceal adenocarcinoma. Phase II trials using cisplatin in both peritoneal mesothelioma and ACC have demonstrated some efficacy indicating potential similarity in the sensitivity of these histologies to cisplatin^{9-12, 16-18}. In our studies, patients with peritoneal mesothelioma achieved an average PFS of 17 months¹⁹ with younger age and completeness of resection being predictive of better outcomes.

1.2.4 Peritoneal carcinomatosis

Peritoneal carcinomatosis represents a formidable treatment challenge in oncology. Once considered a variant of systemic spread of disease, peritoneal carcinomatosis of most histologies is treated with palliative systemic chemotherapy alone, with surgery reserved only for palliation of disease- or treatment for related secondary events such as bowel obstruction and ascites. Systemic multi-drug chemotherapy has not altered the natural history of peritoneal carcinomatosis in more common diseases such as colorectal cancer, as patients suffer disease progression and functional deterioration due to visceral obstruction, malignant ascites and cancer cachexia over a matter of months²⁰⁻²². The biology of peritoneal carcinomatosis is distinctive, unlike hematogenous metastasis. Insights into the natural history of peritoneal tumor dissemination have engendered novel multi-modality treatment approaches to this challenging clinical problem. Tumor dissemination across peritoneal surfaces occurs through established mechanisms of direct tumor extension; tumor cell spread in peritoneal fluid, and malignant peritoneal seeding from surgical manipulation of the tumor, and can occur in the absence of regional or distant nodal or systemic metastases.

Adrenal neoplasms are one of the most common of all human tumors²³. The prevalence of adrenal incidentaloma is approximately 5% on abdominal imaging, but can be as high as 10% in the elderly. As the U.S. population ages, the management of adrenal incidentaloma will be an increasingly important issue in health care²³. There are no reliable preoperative clinical, imaging or biochemical tests available to distinguish between primary benign and malignant adrenocortical neoplasms in the absence of obvious metastatic disease or locoregional invasion²⁴. Imaging features such as tumor heterogeneity, irregular tumor border, hemorrhage, necrosis, rapid tumor growth rate, tumor Hounsfield unit >10-20 on non-contrast CT scan, and intravenous contrast washout of 40% or less after 15 minutes are more common in malignant tumors but are not reliable enough to avoid the need for adrenalectomy to exclude a cancer diagnosis nor to forgo continued follow up²⁴⁻²⁹. The majority of patients undergo laparoscopic adrenalectomy for diagnosis. ACC cannot be diagnosed by frozen section (postoperative histopathologic examination to distinguish between malignant and benign primary adrenal tumors is difficult) and thus peritoneal seeding from surgical manipulation is a particular problem with ACC as the procedure is performed without a tumor diagnosis^{30, 31}.

According to a recent publication, the rate of peritoneal carcinomatosis following laparoscopy is 30% at center experienced in laparoscopic procedures and 16% following open adrenalectomy. A European study suggests the 4 year rate of peritoneal carcinomatosis is 67% for laparoscopy and only 27% for open adrenalectomy. Due to increasing use of laparoscopy, this has evolved as a significant problem for patients with metastatic adrenocortical cancer. The clinical sequela is vexing as the peritoneum is a surface that is not well penetrated by traditional systemic intravenous chemotherapy. Hyperthermia alone has been shown to be toxic to malignant cells and we have previously combined cisplatin and hyperthermia in prior protocols safely.

1.2.5 Surgical metastasectomy

Surgical metastasectomy has been used extensively for ACC in our institution. Our published data and experience demonstrates the ability to safely perform this surgery and to prolong disease free interval to greater than a year in selected patients³². Combining surgery with Cisplatin, the drug most effective in ACC, seems like a logical direction for the treatment of this histology where the bulk of tumor is intraperitoneal. The purpose of this trial is to determine if an aggressive surgical approach with intraperitoneal administration of heated cisplatin when tumor volume is minimal, can impact and improve on progression free survival.

Given the aggressive treatment regimen and the aggressive nature of the diseases, it is important to understand the impact this therapy has on patients' health related quality of life. As a secondary endpoint we will therefore evaluate patients' health related quality of life prior to therapy and at intervals following recovery from the surgery and HIPEC. The goal of tracking quality of life is while surgery may temporarily negatively impact on QOL, it is our hope that it would rebound to better than pre-op if this approach has any merit and utility in the care of patients in the future.

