2.2.2 Within 4 weeks prior to treatment

- Baseline imaging: CT scan of chest, abdomen and pelvis (CT C/A/P) with triphasic 1mm cuts as per the liver scan protocol. For patients with evidence of hepatic disease, a baseline MRI-L will be performed.
- Completion of Health Related Quality of Life Forms (HRQOL)

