3.10 POST DISCHARGE

- CBC weekly following discharge or until toxicities have resolved (less than grade 3 or baseline) and patient has recovered from nadir. This may be done through the patient's referring physician with the results faxed to [name] or her designee.
- Patients will return to clinic approximately 4-8 weeks following surgery for their 1st post-operative visit and will be followed as clinically indicated until recovery. Upon recovery from the surgical procedure, the following end of treatment evaluations will be performed:
 - Imaging studies to establish new baseline
 - Tumor markers as indicated
 - CBC, acute care, mineral and hepatic panel, CRP, Albumin, pre-albumin, ferritin, Hgb A1c if elevated pre-op.
 - Physical examination to include ECOG, weight and vital signs
 - QOL survey

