3.12 MEASUREMENT OF HEALTH RELATED QUALITY OF LIFE

Baseline Quality of Life Questionnaires (QOL) will be completed prior to the surgical procedure during the first follow up visit [following recovery from the surgical procedure] approximately one year following the procedure or at the time off study.

Patients will be informed of the details of the QOL part of this study and reassured that their decision to participate will not affect their participation in the protocol. Once enrolled, the patient has the right at any time to elect not to continue completing the questionnaires. In the event a patient goes off study prior to completion of the follow up time points, the data gathered from their completed QOL questionnaires will be included in the final analysis.

Measures will be initially administered by the Associate Investigator Research Nurse or designee prior to randomization. The Research Nurse will assess the patient's ability to read, and if the patient is unable to read, it will not be administered. The Research Nurse or designee will administer the questionnaires providing a firm surface at a table or a clipboard and a pencil. The patients will be directed to complete the questionnaires using the following instructions:

We would like to better understand how you and other persons in this study feel, how well you are able to do your usual activities, and how you rate your health while you are participating in this research study. To help us better understand these things about you and other persons participating in this study please complete this questionnaire about your quality of life. This questionnaire should not take longer than 15 minutes to complete.

The questionnaire is simple to fill out. Be sure to read the instructions on the top of the questionnaire. Remember, this is not a test and there are no right or wrong answers. Choose

the response that best represents the way you feel. I will quickly review the questionnaire when you are done to make sure that all the items have been completed. Please answer all the items with the response that is most applicable.

You should answer these questions by yourself. Your husband/wife or other family members or friends should NOT assist you in completing the questionnaire. Please fill out the questionnaire now. Return the questionnaire to me when you have completed it. We will be asking you to complete this again during some of your follow up visits. If you have any questions, please ask.

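### The first post-operative QOL form is triggered by recovery rather than time since surgery, so the first value and any claim about early or whole-course impact are selective and likely optimistic

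*Combined protocol and SAP*

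**What the plan says.** Section 1.1.2 makes it a secondary objective to "Determine the impact of surgery and HIPEC on QOL". Section 1.2.5 sets out what is expected: "while surgery may temporarily negatively impact on QOL", followed by recovery, since "it is our hope that it would rebound to better than pre-op". Section 2.2.2 places the baseline form within 4 weeks before treatment.

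Three sections make the first post-operative form depend on recovery:

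- Section 1.2.5 plans assessment "prior to therapy and at intervals following recovery from the surgery and HIPEC".
- Section 3.10 first says "Patients will return to clinic approximately 4-8 weeks following surgery for their 1st post-operative visit", with further visits as needed until the patient has recovered. It then says "Upon recovery from the surgical procedure, the following end of treatment evaluations will be performed" and puts the QOL survey in that list. It neither defines recovery nor gives a latest date for the survey.
- Section 3.12 places the form "during the first follow up visit [following recovery from the surgical procedure" (the bracket closes there in the protocol), and then at about one year or when the patient leaves the study.

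Section 3.11 works differently. Its visits count from the operative date, every 3 months +/- 1 month in year one, with a form at the first follow-up visit and at each later evaluation. It states no recovery condition. Sections 3.11 and 3.12 also ask for a form when a patient goes off study; before one year, section 3.11 asks for it only where possible. Appendix C describes the instrument, FACT-C, as covering the past seven days and taking about 10 minutes. Section 8 contains no QOL analysis.

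**The concern.** The protocol predicts a temporary loss of QOL after surgery and then schedules the first form for when that loss has passed. The timing of the measurement depends on the outcome being measured. A patient with a fistula, an abscess or a long stay may attend at 4-8 weeks without a form being due, while a patient who has recovered smoothly completes one. Because FACT-C looks back only seven days, a later form cannot reconstruct the missed period.

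At stake is what the trial can say about the early QOL cost of an aggressive procedure. A favourable first value could partly reflect who was asked and when.

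**Working it through.** **Plan's own figure.** The documents give no QOL mean, standard deviation, expected fall or recovery time, so there is no QOL figure to reproduce. The only sample-size figure is the 80% power in section 8 for median PFS of 10 against 5 months (24 patients, one-sided alpha 0.10). With exponential PFS, the proportion progression-free at 5 months is p0 = 0.5 under the null and p1 = 0.5^(5/10) = 0.7071 at the target. Power = Phi([(0.7071 - 0.5) x sqrt(24) - 1.2816 x 0.5] / sqrt(0.7071 x 0.2929)) = Phi(0.82) = 79.4%. The stated figure reproduces, and nothing below affects it.

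**Step 1: what is scheduled when.**

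| Time | Recovered patient | Unrecovered patient |
|---|---|---|
| Within 4 weeks before treatment | Form | Form |
| About 4-8 weeks after surgery (3.10) | Form | Visit, no form due |
| 3 months +/- 1 month, so 2-4 months (3.11) | Form | Form |
| Later 3.11 visits and off study | Form | Form |

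The selection is confined to the second row.

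**Step 2: effect on the first value.** Let f be the share unrecovered at the 4-8 week visit, d their FACT-C deficit against recovered patients, and m the mean in recovered patients. The mean over everyone is (1 - f) x m + f x (m - d) = m - f x d. The recovery-triggered form yields m. The overstatement is f x d. Both inputs are assumptions, with f from 10% to 40% and d from 5 to 20 points:

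| f | d = 5 | d = 10 | d = 20 |
|---|---|---|---|
| 10% | 0.5 | 1.0 | 2.0 |
| 20% | 1.0 | 2.0 | 4.0 |
| 30% | 1.5 | 3.0 | 6.0 |
| 40% | 2.0 | 4.0 | 8.0 |

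This is the full effect when unrecovered patients are left out of the first value, or are asked later and then score like recovered patients. If they are asked later having improved only partly, the overstatement lies between 0 and f x d.

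**Step 3: effect on a whole-course average.** Assume a fall of D points that recovers linearly over w weeks and is missed entirely. The 12-month average is then overstated by D x w / 2 / 52. For D = 5 and w = 4 this is 5 x 4 / 104 = 0.2 points; for D = 20 and w = 13 it is 20 x 13 / 104 = 2.5 points. The upper value is a ceiling, because the form at 2-4 months would catch part of a 13-week fall.

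**Step 4: effect on a later visit against baseline.** That comparison uses the later form and the baseline form only. The 4-8 week value does not enter it, so its absence causes no shift.

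**The case against.** The strongest reply is that section 3.11 limits the problem. From 2-4 months, forms follow the calendar, so a patient who is still unwell is asked while unwell, and the off-study form reaches some who never recover. The QOL comparison the protocol describes, a rebound above the pre-operative level, concerns those later visits. All of this stands.

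A reader might infer that the QOL result as a whole is biased upward. The documents do not support that. Section 8 defines no QOL summary, time point or estimand, so there is no single result whose bias could be signed, and step 4 shows that later comparisons are unaffected. Nor do they support the inference that unrecovered patients are always asked only once well: section 3.11 sets no such condition.

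It can also be said that recovery is undefined, that the bracket in section 3.12 may merely identify a visit, and that no text forbids giving an unwell patient the form at 4-8 weeks. That is fair as to practice. But three sections use recovery as the trigger, and section 3.10 separates the dated visit from the evaluations done on recovery. In the other direction, the time points listed in section 3.12 would, taken alone, make the recovery-triggered form the only scheduled one between baseline and about a year for a patient who stays on study. Section 3.12 itself refers to section 3.11 for later visits, so the fuller schedule is the better reading.

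Morbidity is a separate secondary objective, and abscess, fistula and stays over 14 days are captured at any grade (6.3.1). Those records identify the patients concerned but do not measure their QOL.

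**Conclusion.** The concern holds for the first post-operative value and for any claim about early or whole-course QOL impact: these are selective and likely optimistic. It does not extend to the operative-date forms from about 3 months or to later-visit-versus-baseline comparisons.

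The size is not derivable from the documents. The range of about 0.5-8 FACT-C points rests entirely on the assumed 10-40% unrecovered and 5-20 point deficit, and on unrecovered patients being absent from the first value or scoring like recovered patients by the time they are asked. The direction is likely rather than certain: it presumes that unrecovered patients feel worse at 4-8 weeks than when eventually asked, which would fail for a patient in steady decline.

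This affects a secondary objective. The primary PFS analysis and its sample size are untouched.

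**What to change.** In sections 1.2.5, 3.10 and 3.12, remove recovery as the trigger for the QOL form. Give FACT-C to every patient at the 4-8 week first post-operative visit whatever their recovery status, and then at the operative-date visits of section 3.11. State in section 8 that change from baseline will be analysed by time since surgery. While editing section 3.12, make clear which visit is the first follow-up visit. Leave the other evaluations done on recovery as they are.

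The cost is small: wording changes, no added visit or staff, and a form of about 10 minutes at a visit already planned. Expect a few more incomplete forms from unwell patients and a less favourable early value.

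The change has a limit that the plan should state. With seven-day recall, a form at 4-8 weeks still misses the hospital stay (about 7-14 days under section 3.9) and the first weeks after it. The trial should not claim to estimate the full depth of the QOL loss.
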